#### **19.1.2 Primary analysis**

- Population: FAS
- Stratification: Table: Descending frequency of SOC and descending frequency of PT within each SOC.
- Statistics: The incidence of TEAEs and its characteristics (i.e., Ocular and systemic AEs, Suspected treatment emergent AEs related to the study medication, Serious treatment emergent AEs, TEAEs leading to Death, TEAEs leading to discontinuation of study,) will be summarised for table as number of patients (n), percentages (%) and number of events (m). TEAEs will also be summarized by primary system organ class, preferred term and severity.

#### 20. Secondary endpoint assessments

The secondary endpoints will evaluate the effectiveness of brolucizumab.

20.1 Mean change in BCVA from baseline to week 16 and week 56 as measured by Early Treatment Diabetic Retinopathy Study (ETDRS) letters

#### 20.1.1 Variables and derivations

Variables:

• Total Visual Acuity Score (ETDRS letters)

Derivations:

- Time Frame: Baseline to week 16 and Baseline to week 56.
- If the question "select the Assessment" is answered as "Total Visual Acuity Score (ETDRS letters)" from BCVA form of eCRF then corresponding results will be used from total Visual Acuity Score (ETDRS letters) for study eye.

Population:	For Table: FAS
	For Listing: SCR
Stratification:	Table: NA
	Listings: By patient no. and date of test
Statistics:	The summary statistics for absolute and absolute change
	from baselines will be presented in the table as number of
	observations (n), arithmetic mean, standard deviation (SD),
	lower quartile, median, upper quartile, minimum and
	maximum. Point estimate, Two-sided 95% confidence
	intervals and p-values for within-patient changes across time
	will be presented using paired t-test. The listing will be
	presented.

# 20.2 Percentage (%) of patient eyes with gain in BCVA of 15/10/5 ETDRS letters or more at week 16 and week 56

#### 20.2.1 Variables and derivations

Variables:

• Total Visual Acuity Score (ETDRS letters)

#### Derivations:

- If the question "select the Assessment" is answered as "Total Visual Acuity Score (ETDRS letters)" from BCVA form of eCRF then corresponding results will be used from total Visual Acuity Score (ETDRS letters) for study eye as appropriate.
- Below mentioned categories will be derived as follows:
  - Gain in BCVA of 15 ETDRS letters: If the Total Visual Acuity Score (ETDRS letters) >= 15 ETDRS letters then corresponding patients will be considered as "Gain"
  - Gain in BCVA of 10 ETDRS letters: If the Total Visual Acuity Score (ETDRS letters) >= 10 ETDRS letters then corresponding patients will be considered as "Gain"
  - Gain in BCVA of 5 ETDRS letters: If the Total Visual Acuity Score (ETDRS letters) >= 5 ETDRS letters then corresponding patients will be considered as "Gain"

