#### 7.1.2 Secondary Endpoints

- 1.1 Mean change in BCVA from baseline to week 16 and week 56 as measured by Early Treatment Diabetic Retinopathy Study (ETDRS) letters.
- 1.2 Percentage (%) of patient eyes with gain in BCVA of 15/10/5 ETDRS letters or more from baseline to week 16 and week 56.
- 1.3 Percentage (%) of patient eyes with loss in BCVA of 15/10/5 ETDRS letters or more from baseline to week 16 and week 56.
- 2. Number of anti-VEGF injections, non-injection visits, and total number of visits during the 56 weeks of treatment with brolucizumab.
- 3.1 Percentage (%) of patient eyes with at least one duration of interval between injections  $\geq 8$  weeks but <12 weeks.
- 3.2 Percentage (%) of patient eyes with at least one duration of interval between injections  $\geq 12$  weeks.
- 4.1 Absence of intra-retinal fluid from baseline to week 16 and week 56.
- 4.2 Absence of sub-retinal fluid from baseline to week 16 and week 56.
- 5. Estimate CST change from baseline (in  $\mu$ m) to week 16 and at week 56.

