#### 3.2 Secondary endpoints

- 1a. Mean change in BCVA from baseline to week 16 and week 56 as measured by Early Treatment Diabetic Retinopathy Study (ETDRS) letters.
- 1b. Percentage (%) of patient eyes with gain in BCVA of 15/10/5 ETDRS letters or more from baseline to week 16 and week 56.
- 1c. Percentage (%) of patient eyes with loss in BCVA of 15/10/5 ETDRS letters or more from baseline to week 16 and week 56.
- 2. Number of anti-VEGF injections, non-injection visits and total number of visits during the 56 weeks of treatment with brolucizumab.
- 3a. Percentage (%) of patient eyes with at least one duration of interval between injections ≥ 8 weeks but <12 weeks.

3b. Percentage (%) of patient eyes with at least one duration of interval between injections  $\geq$  12 weeks.

- 4a. Absence of intra-retinal fluid from baseline to week 16 and week 56.
- 4b. Absence of sub-retinal fluid from baseline to week 16 and week 56.
- 5. Estimate CST change from baseline (in  $\mu$ m) to week 16 and at week 56.

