#### Stratification: Table: NA

Statistics: Number of patient (n) and percentage (%) will be presented for patient eyes with gain in BCVA of 15, 10 and 5 ETDRS letters categories or more at week 16 and week 56 in table.
95% Confidence interval will be calculated and presented using Clopper Pearson test.
## 20.3 Percentage (%) of patient eyes with loss in BCVA of 15/10/5 ETDRS letters or more at week 16 and week 56

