#### Derivations:

- If the question "select the Assessment" is answered as "Total Visual Acuity Score (ETDRS letters)" from BCVA form of eCRF then corresponding results will be used from total Visual Acuity Score (ETDRS letters) for study eye.
- Below mentioned categories will be derived as follows:
  - Loss in BCVA of 15 ETDRS letters: If the Total Visual Acuity Score (ETDRS letters) < 15 ETDRS letters then corresponding patients will be considered as "Loss"
  - Loss in BCVA of 10 ETDRS letters: If the Total Visual Acuity Score (ETDRS letters) < 10 ETDRS letters then corresponding patients will be considered as "Loss"
  - Loss in BCVA of 5 ETDRS letters: If the Total Visual Acuity Score (ETDRS letters) < 5 ETDRS letters then corresponding patients will be considered as "Loss".

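### As written, SAP 20.2 and 20.3 classify BCVA gain and loss from the letter score at the visit, not from change since baseline, and the loss rule is wrong on any reading

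*SAP*

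**What the plan says.** The endpoints are defined relative to baseline. SAP 3.2 has, for gain, "Percentage (%) of patient eyes with gain in BCVA of 15/10/5 ETDRS letters or more from baseline to week 16 and week 56". Protocol 7.1.2 has, for loss, "Percentage (%) of patient eyes with loss in BCVA of 15/10/5 ETDRS letters or more from baseline to week 16 and week 56". Each document gives both endpoints in this form.

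The derivations differ. The only variable that SAP 20.2.1 names is "Total Visual Acuity Score (ETDRS letters"), taken from the BCVA form for the study eye. The gain rule at the top threshold is "If the Total Visual Acuity Score (ETDRS letters) >= 15 ETDRS letters then corresponding patients will be considered as 'Gain", and at the bottom threshold "If the Total Visual Acuity Score (ETDRS letters) >= 5 ETDRS letters then corresponding patients will be considered as 'Gain"; the 10-letter rule has the same form. SAP 20.3.1 uses the same variable for loss: "If the Total Visual Acuity Score (ETDRS letters) < 15 ETDRS letters then corresponding patients will be considered as 'Loss", again repeated at 10 and 5.

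Neither section mentions baseline or defines a change variable, and the headings of 20.2 and 20.3 speak only of the two visits. Change from baseline does appear in SAP 20.1, where the mean BCVA analysis asks for "The summary statistics for absolute and absolute change" from baseline, and in SAP 20.9 for CST. It is not carried into 20.2 or 20.3. For both percentages the SAP then plans: "95% Confidence interval will be calculated and presented using Clopper Pearson test".

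**The concern.** A threshold of 15, 10 or 5 letters makes sense as a size of change. Applied to the score itself, it asks only whether the eye can still read a handful of letters, which most study eyes will do whatever happened to them during the trial. The loss rule has a second fault: it is the plain complement of the gain rule, with no negative sign.

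Two protocol-defined secondary endpoints are affected, each at three thresholds and two time points: 2 × 3 × 2 = 12 reported percentages, with their confidence intervals. SAP 20.3 is also the only place where the plan counts the eyes that lost a given number of letters. In addition, the protocol intends a descriptive comparison of the results with the two phase 3 trials, and responder percentages built on a different quantity could not be compared.

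**Working it through.** The documents state no expected gain or loss percentage, so there is no figure to reproduce. The check applies the written rules and the endpoint definition to the same eyes.

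**Step 1. The rules themselves (no data needed).** Let S be the study-eye score at the visit, B the baseline score, C = S − B, and k = 15, 10 or 5.

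- Endpoint definition: gain if C ≥ k; loss if C ≤ −k.
- SAP, literal reading: gain if S ≥ k; loss if S < k.
- SAP, change-score reading: gain if C ≥ k; loss if C < k.

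| Eye (B → S) | C | Endpoint definition | SAP, literal | SAP, change-score reading |
|---|---|---|---|---|
| 70 → 50 | −20 | loss at 15, 10, 5 | gain at 15, 10, 5 | loss at 15, 10, 5 |
| 60 → 60 | 0 | neither | gain at 15, 10, 5 | loss at 15, 10, 5 |
| 50 → 60 | +10 | gain at 10, 5 | gain at 15, 10, 5 | loss at 15; gain at 10, 5 |
| 8 → 14 | +6 | gain at 5 | loss at 15; gain at 10, 5 | loss at 15, 10; gain at 5 |

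On either SAP reading, loss is exactly 100% minus gain at the same k, so no eye can be stable. The ordering of the loss categories is also reversed. A value below 5 is always below 15, so the reported loss of 15 can never be rarer than the reported loss of 5. A true loss of 15 can never be more common than a true loss of 5.

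**Step 2. Hand calculation under a normal model.** The mean change of +6.6 letters is the Week 48 figure for 6 mg in the first phase 3 trial (Protocol section 5). The documents give no SD of change; 10, 12 and 15 are assumed.

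- True gain ≥ 15: P(C ≥ 15) = 1 − Φ((15 − 6.6)/SD) = 0.200, 0.242, 0.288.
- True loss ≥ 15: P(C ≤ −15) = Φ((−15 − 6.6)/SD) = 0.015, 0.036, 0.075.
- Loss of 15 on the change-score reading: P(C < 15) = 0.800, 0.758, 0.712.
- Gain of 15 on the literal reading, with assumed score distributions at the visit: P(S ≥ 15) = 0.960 for N(50, SD 20), 0.977 for N(55, SD 20), 0.999 for N(60, SD 15), and above 0.999 for N(65, SD 15).

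**Step 3. Wider range by simulation.** Eligibility sets no BCVA limits, so poorer baselines were included. Assumed: baseline mean 35, 45, 55 or 60; baseline SD 12 or 18; SD of change 10 or 15. Mean change is +6.75, the midpoint of +6.6 and +6.9 for 6 mg in the two phase 3 trials. One million eyes were simulated per scenario, with scores rounded and held to 0–100. Ranges run over all 16 scenarios.

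| Percentage of eyes | k = 15 | k = 10 | k = 5 |
|---|---|---|---|
| True gain | 20.2–30.3 | 37.4–42.8 | 54.7–59.0 |
| Gain, SAP literal | 88.0–100.0 | 91.9–100.0 | 94.8–100.0 |
| True loss | 1.5–7.8 | 4.8–13.9 | 12.5–22.7 |
| Loss, SAP literal | 0.0–12.0 | 0.0–8.1 | 0.0–5.2 |
| Loss, change-score reading | 69.7–79.8 | 57.2–62.6 | 41.0–45.3 |
| Share of true losers coded as loss, SAP literal | 1.4–49.4 | 0.2–27.3 | 0.0–14.6 |

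The last row depends heavily on baseline acuity. At k = 15 it is 1.4–14.5% when baseline mean is 55–60, and 15.5–49.4% when it is 35–45.

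**Step 4. Confidence intervals.** With N = 105, 105 eyes coded as gain gives a Clopper-Pearson 95% interval of 96.5–100%. If the true count were 30 of 105 (28.6%), the interval would be 20.2–38.2%. The intervals do not overlap, so the planned interval would convey precision around the wrong quantity.

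**The case against.** The strongest reply is that the intent is clear. Both endpoint lists refer to baseline, Protocol 7.6.5 introduces the secondary analyses as change from baseline, and SAP section 5 says the analysis will follow the protocol. A careful programmer would subtract baseline, and a table with nearly 100% gain would probably be questioned. This makes the harm conditional on literal programming, but it does not supply a rule. The SAP says it sets out the rules for the analysis, and on this point it contradicts its own endpoint list. The change-score table, with plausible gain percentages, would also be less likely to raise an alarm.

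Second, if the score is shorthand for change, the gain rule is correct and only the loss endpoint fails. That is right. The loss rule is still wrong at every threshold on that reading.

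Third, losses would not vanish altogether. On the literal rule an eye that ends below the threshold is coded as a loss, though because of where it ended and not how far it fell. SAP 20.1 still reports the quartiles and minimum of change and lists BCVA by patient, and ocular changes meeting the AE definition are captured as adverse events. This stands: losses would be mostly miscoded, not erased, and the primary safety endpoint is untouched.

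Fourth, these are descriptive secondary percentages in a single-arm study, no success criterion depends on them, and the raw scores are kept. This limits the consequence and makes correction easy, but it is no reason to leave the rule as it is.

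**Conclusion.** The concern holds, and the rules must be corrected before they are used. The loss rule is wrong on both possible readings, and the gain rule is wrong as literally written. These conclusions follow from the inequalities and need no assumed data.

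The size does rest on assumptions, because the documents give neither a baseline BCVA distribution nor an SD of change. Over the ranges tried, the literal rule would report 88–100% of eyes gaining 15 letters, where the endpoint definition gives about 20–30%. The change-score reading would report about 70–80% of eyes losing 15 letters, where the definition gives about 1.5–8%. The mean change is a Week 48 phase 3 figure, used here only for illustration.

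**What to change.** Replace the derivations in SAP 20.2.1 and 20.3.1 with the following:

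- CHG = study-eye letter score at the visit (week 16 or week 56) minus the study-eye baseline score, with baseline as already defined in SAP 7.2.
- Gain of at least 15/10/5 letters: CHG ≥ 15, ≥ 10, ≥ 5.
- Loss of at least 15/10/5 letters: CHG ≤ −15, ≤ −10, ≤ −5.

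Eyes meeting neither condition at a threshold stay in the denominator and need no label of their own; calling them unchanged would mislead for an eye at +12. Restore the reference to baseline in the headings of 20.2 and 20.3. The Clopper-Pearson intervals and the missing-data rule in SAP 8.2 are unaffected by this change.

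The cost is two SAP paragraphs, an entry in the revision history and the matching programs. No data collection changes.

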#### 20.2.2 Analysis

Population: FAS

#### Stratification: Table: NA

Statistics: Number of patient (n) and percentage (%) will be presented for patient eyes with gain in BCVA of 15, 10 and 5 ETDRS letters categories or more at week 16 and week 56 in table.
95% Confidence interval will be calculated and presented using Clopper Pearson test.
## 20.3 Percentage (%) of patient eyes with loss in BCVA of 15/10/5 ETDRS letters or more at week 16 and week 56

#### 20.3.1 Variables and derivations

Variables:

• Total Visual Acuity Score (ETDRS letters)

#### Derivations:

- If the question "select the Assessment" is answered as "Total Visual Acuity Score (ETDRS letters)" from BCVA form of eCRF then corresponding results will be used from total Visual Acuity Score (ETDRS letters) for study eye.
- Below mentioned categories will be derived as follows:
  - Loss in BCVA of 15 ETDRS letters: If the Total Visual Acuity Score (ETDRS letters) < 15 ETDRS letters then corresponding patients will be considered as "Loss"
  - Loss in BCVA of 10 ETDRS letters: If the Total Visual Acuity Score (ETDRS letters) < 10 ETDRS letters then corresponding patients will be considered as "Loss"
  - Loss in BCVA of 5 ETDRS letters: If the Total Visual Acuity Score (ETDRS letters) < 5 ETDRS letters then corresponding patients will be considered as "Loss".

#### 20.3.2 Analysis

Population:	FAS
-------------	-----

#### Stratification: Table: NA

Statistics: Number of patient (n) and percentage (%) will be presented for patient eyes with loss in BCVA of 15, 10 and 5 ETDRS letters categories or more at week 16 and week 56 in table.
 95% Confidence interval will be calculated and presented using Clopper Pearson test.

## 20.4 Number of anti-VEGF injections, non-injection visits, and total number of visits during the 56 weeks of treatment with brolucizumab.

#### 20.4.1 Variables and derivations

Variables:

- Date of Brolucizumab Administration
- Date of Visit

#### Derivations:

 The total number of Brolucizumab anti-VEGF injections and non-injection visits will be calculated using Brolucizumab dosing form of eCRF if the date of Brolucizumab Administration is not missing on the respective treatment visit then count of injection =1, it will be calculated for all treatment visits and then sum will be calculated to get the number of anti-VEGF injections for respective patient.

#### 20.4.2 Analysis

Population:	For Table: FAS	
	For Listing: SCR	
Stratification:	Listing: By patient no. and visit.	
Statistics:	Number of anti-VEGF injections, non-injection visits, and total	
	number of visits during the 56 weeks of treatment with	
	brolucizumab will be presented in listing.	

## 20.5 Percentage (%) of patient eyes with at least one duration of interval between injections ≥ 8 weeks but <12 weeks

#### 20.5.1 Variables and derivations

Variables:

- Date of Brolucizumab Administration
- Dosing Schedule (q8w dosing)

#### Derivations:

If the question from eCRF "Select Dosing Schedule" is answered as "q8w Dosing" and the duration of interval between injections is 8 to 11 weeks.

#### 20.5.2 Analysis

Population: FAS

Stratification: Table: NA

Statistics: Number of patient (n) and percentage (%) will be summarised for the patient eyes with at least one duration of interval between injections ≥ 8 weeks but <12 weeks.

## 20.6 Percentage (%) of patient eyes with at least one duration of interval between injections ≥ 12 weeks

#### 20.6.1 Variables and derivations

Variables:

- Date of Brolucizumab Administration
- Dosing Schedule (q12w dosing)

#### Derivations:

If the question from eCRF "Select Dosing Schedule" is answered as "q12w Dosing" and the duration of interval between injections is above or equal to 12 weeks.

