#### Secondary Endpoints Analysis

The secondary endpoints will evaluate the effectiveness of brolucizumab in terms of change in the following parameters from Baseline to the end of week 56. BCVA at baseline, week 16 and 56 including the change will be summarized with standard descriptive statistics.

- Mean change in BCVA from baseline to week 16 and week 56 as measured by ETDRS letters.
- Percentage (%) of patient eyes with gain in BCVA of 15/10/5 ETDRS letters or more at week 16 and week 56
- Percentage (%) of patient eyes with loss in BCVA of 15/10/5 ETDRS letters or more at week 16 and week 56.
- Number of anti-VEGF injections, non-injection visits and total number of visits
- Percentage (%) of patient eyes with at least one duration of interval between injections ≥ 8 weeks but <12 weeks.

- Percentage (%) of patient eyes with at least one duration of interval between injections ≥ 12 weeks.

- Percentage of patients with absence of intra-retinal fluid from baseline to week 16 and week 56.
- Percentage of patients with absence of sub-retinal fluid from baseline to week 16 and week 56.
- Estimated change in CST (in µm) from baseline to week 16 and week 56.

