#### 5. Changes/deviations from the planned analysis

Analysis will be performed as per planned protocol however, if any deviation in implementing original statistical plan will be described and justified in the clinical study report.

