#### 20.6.2 Analysis

Population: FAS

Stratification: Table: NA

Statistics: Number of patient (n) and percentage (%) will be summarised for the patient eyes with at least one duration of interval between injections ≥ 12 weeks.

## 20.7 Percentage of patients with absence of intra-retinal fluid (IRF) from baseline to week 16 and week 56

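### SAP 20.5.1 and 20.6.1 add a dosing-schedule condition to interval endpoints 3.1 and 3.2, which the protocol and the SAP's own headings define by interval length alone

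*SAP*

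**What the plan says.** **Length alone.** Protocol 7.1.2 states both endpoints as "Percentage (%) of patient eyes with at least one duration of interval between injections" followed by a length band: at least 8 but under 12 weeks for 3.1, and at least 12 weeks for 3.2. Protocol 7.6.5 repeats this, for example "Percentage (%) of patient eyes with at least one duration of interval between injections ≥ 12 weeks". SAP 3.2 lists 3a as "Percentage (%) of patient eyes with at least one duration of interval between injections ≥ 8 weeks but <12 weeks". The statistics lines agree: SAP 20.5.2 reports "patient eyes with at least one duration of interval between injections ≥ 8 weeks but <12 weeks" and SAP 20.6.2 reports "patient eyes with at least one duration of interval between injections ≥ 12 weeks".

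**Length plus regimen.** The derivations differ. SAP 20.5.1 (endpoint 3.1) reads "Select Dosing Schedule' is answered as 'q8w Dosing' and the duration of interval between injections is 8 to 11 weeks". SAP 20.6.1 (endpoint 3.2) reads "Select Dosing Schedule' is answered as 'q12w Dosing' and the duration of interval between injections is above or equal to 12 weeks". Both subsections also list the dosing schedule as a variable.

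**Declared changes.** SAP 5 says "Analysis will be performed as per planned protocol however" any deviation will be described in the study report. It names none.

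**Schedule.** Protocol 7.2 places q8w injections at Weeks 16, 24, 32, 40 and 48 and q12w injections at Weeks 20, 32 and 44, after loading at Weeks 0, 4 and 8. Re-allocation between regimens is at the investigator's discretion. Table 7-1 gives each visit from Week 4 to Week 48 a window of ±1 week.

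**The concern.** The same table can be programmed in two ways. A programmer who follows the heading and the statistics line uses injection dates only. One who follows the derivation also filters on the eCRF schedule answer. The two can report different percentages for 3.1 from identical data, under the same title. A reader could not tell whether the result means that an eye had an interval of 8 to under 12 weeks or that it was on the q8w regimen.

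Under the derivations, two kinds of interval that the protocol counts fall into neither endpoint:

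- a q12w-labelled interval shorter than 12 weeks, which can occur with every visit inside its window;
- a q8w-labelled interval of 12 weeks or more, for example after one missed injection.

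The SAP also leaves open which visit's label belongs to an interval after re-allocation, whether the interval from Week 8 to the first post-loading injection counts, whether intervals within the loading phase count, and how days become weeks.

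**Working it through.** The documents give no expected value for 3.1 or 3.2, so there is no planned figure to reproduce.

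**Inputs.** Injection weeks come from Protocol 7.2 and windows from Table 7-1. Visit timing, the missed-injection rate and the q12w share in this study are not given, so they are assumed and varied.

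**1. Possible interval lengths.** Each visit may deviate by −7 to +7 days.

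- q12w on schedule: 84 ± 14 = 70 to 98 days.
- q8w on schedule: 56 ± 14 = 42 to 70 days.
- q8w after one missed injection: 112 ± 14 = 98 to 126 days.

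**2. Endpoint 3.1 in q12w eyes.** An eye on q12w throughout has three intervals (Weeks 8–20, 20–32, 32–44) bounded by four visits with deviations e1 to e4. No interval is under 84 days only if e1 ≤ e2 ≤ e3 ≤ e4. If deviations are independent and uniform over 15 whole days:

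P(at least one interval of 70–83 days) = 1 − C(18,4)/15⁴ = 1 − 3060/50625 = 0.940.

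The protocol counts such an eye in 3.1. Under the SAP derivation an eye labelled only q12w never counts.

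Now let a fraction q of visits fall on the exact day and the rest be uniform within ±7 days. With a = (1−q)/15 and z = q + a,

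P(no interval under 84 days) = Σ C(6+i,i)·C(6+j,j)·a^(i+j)·z^(4−i−j), over i, j ≥ 0 with i + j ≤ 4.

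| Visits on the exact day | q12w eyes meeting 3.1 by length but not by the SAP rule |
|---|---|
| 0% (uniform) | 94% |
| 50% | 80% |
| 80% | 45% |
| 90% | 25% |
| 95% | 13% |
| 100% | 0% |

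**3. Effect on the reported 3.1 percentage.** Assume, for illustration only, that 51% to 56% of eyes are on q12w throughout, borrowing the phase 3 figures in Protocol 5. The gap between the rules is then share × proportion:

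- uniform timing: 0.51 × 94.0 = 47.9 to 0.56 × 94.0 = 52.6 points;
- 80% on the exact day: 0.51 × 44.8 = 22.9 to 0.56 × 44.8 = 25.1 points;
- all on the exact day: 0 points.

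**4. Endpoint 3.2.** For eyes labelled q12w throughout, the schedule condition is always met, so the two rules agree. On-schedule q8w intervals are at most 70 days, so they do not reach 84. The rules separate when a q8w injection is missed and a later one is given. With five post-loading injections, each missed independently with probability m,

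P(a missed injection is followed by a later one) = 1 − Σ (1−m)^k · m^(5−k), k = 0 to 5.

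For m = 0.02, 0.05 and 0.10 this is 7.7%, 18.3% and 33.6% of q8w eyes. The protocol counts them in 3.2 and the SAP rule does not.

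**5. The 8-to-11-week range.** Read as completed weeks it is 56 to 83 days, the same as the protocol. Read as exact weeks it is 56 to 77 days, leaving 78 to 83 days in neither class. Rounded to the nearest week it is 53 to 80 days.

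**The case against.** **The condition may be deliberate.** Objective 3 asks about q8w and q12w intervals, Protocol 7.3.4 names the variable in those terms, and the SAP openly lists the dosing schedule as a variable. The condition also stops visit-day variation in q12w eyes from inflating 3.1. This has force as a reason to report a regimen-based result, and SAP 12.1 already tabulates patients dosed under each regimen. It does not justify an undeclared change under an unchanged title.

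**The size is uncertain.** This stands. With near-exact timing and no missed injections or switches, the two rules agree. The derivation lines are also incomplete sentences with no stated consequence, so requiring both conditions is the natural reading rather than an explicit one. The eCRF, which may show at which visit the label is recorded, is not available.

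**Stronger readings that the documents do not support.**

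- A reader might infer that the label makes 3.2 miss on-schedule q12w eyes whose intervals fall under 12 weeks. It does not: those misses come from the protocol's own 12-week cut and occur under both rules.
- A reader might take the 8-to-11-week range as a definite departure. It is only ambiguous. With the q8w condition in place, its upper limit affects no on-schedule interval.
- A reader might expect 3.2 to be set against the phase 3 proportions maintained on q12w. The protocol promises a descriptive comparison with corresponding data but does not name this pairing.

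**Conclusion.** The SAP is wrong as written. Its derivations for 3.1 and 3.2 contradict the protocol, its own endpoint list and its own headings and statistics lines, and the change is not declared. This follows from the text and needs no assumption.

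The size does rest on assumptions. For 3.1, between 0% and 94% of fully dosed q12w eyes are classified differently, depending on how closely visits keep to the exact day. For 3.2 the effect is zero unless q8w injections are missed or much delayed or the regimen is switched; it reaches 7.7% to 33.6% of q8w eyes at 2% to 10% missed per injection. If visits were almost exact but q8w injections were often missed, 3.2 would be the more affected endpoint. The effect of switching cannot be sized, because no rule ties a label to an interval.

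These are secondary, descriptive endpoints with no power claim, so the primary safety conclusion is untouched. The SAP should still be corrected before results are produced.

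**What to change.** 1. In SAP 20.5.1 and 20.6.1, derive both endpoints from injection dates alone, in days: at least 56 and under 84 for 3.1; at least 84 for 3.2.
2. State which intervals count, covering both the interval from Week 8 to the first post-loading injection and intervals within the loading phase. A missed Week 4 injection, for example, leaves a Week 0 to Week 8 interval of 49 to 63 days.
3. Report the regimen-based version separately as a supportive result for Objective 3, using the strata in SAP 7.3, with a rule for which visit's label applies after re-allocation.
4. If the sponsor wants the regimen condition as the main definition, relabel both endpoints and declare the change in SAP 5 before results are produced.

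The cost is SAP wording and a little programming. Injection dates and dosing schedule are already SAP variables, and under steps 1 to 3 the protocol endpoints do not change. The drawback is that 3.1 by length may sit near its ceiling, and that meeting 3.1 or 3.2 does not mean being on q8w or q12w. A footnote to the table should say so.
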